5.5.3. Vital Signs

Vital signs will include measurement of blood pressure (BP) and heart rate (HR): supine (after at least 5-min rest) and standing (after1-min and 3-min standing).

Actual value of BP and HR, between supine and standing (after 1-min and 3-min standing) at each visit (timepoint if applicable) will be presented using descriptive statistics by treatment group. A figure with the mean (\pm SD) of vital sign parameters by visit will be displayed.

Number of subjects with changes in HR (> 20 and > 30) will be presented at baseline and each post-baseline visit. The risk difference between treatment arms vs placebo, and 95% confidence interval will be calculated.

A separate table with a decrease in systolic BP > 20 mmHg, or diastolic > 10 mmHg on standing from supine position will be presented at baseline and each post-baseline visit. The risk difference between treatment arms vs placebo, and 95% confidence interval will be calculated.

Percentage of patients with maximum systolic BP by category of BP post-baseline (< 90, \geq 90, \geq 120, \geq 140, \geq 160, and \geq 180) will be presented.

Percentage of patients with maximum diastolic BP by category of BP post-baseline (< 60, > 60, > 90, > 110, and > 120) will be presented.

All vital signs data will be presented in a data listing.

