3. GENERAL STATISTICAL CONSIDERATIONS

3.1. General Methods

Statistical analysis will be performed using SAS® software Version 9.4 or later (SAS 2001).

For continuous variables, descriptive statistics will include the number of subjects (n), mean, SD, median, minimum, and maximum. Frequencies and percentages will be displayed for categorical data. Percentages by categories will be based on the number of subjects including missing data, ie, will add up to 100%.

The estimated mean and median for a set of values should be calculated to one more decimal place than the raw (observed) data and rounded appropriately. Standard errors (SE) (or SD) should be calculated to two decimal places beyond the raw (observed) data and rounded appropriately. The decimal place for minimum and maximum should be the same as raw (observed) data. Percentage values should be reported with one digit to the right of the decimal point. When numerator value is "0," it should be displayed as "0." Further, a maximum of two decimal places will be used for all summary statistics unless otherwise specified.

Summaries presented by visit will be based on the scheduled assessments as planned in the protocol. Unscheduled assessments will not be included in the by-visit summary tables, however, will be included in the listings. Any unscheduled visit that falls within a visit window period without a scheduled visit will be used in summary tables. The summary tables and listings will be presented by DGM4 status (positive/negative) where noted, treatment group, and overall. The treatment groups are defined as:

- Placebo QD
- Liafensine 1 mg QD
- Liafensine 2 mg QD
- Liafensine 1 mg and 2 mg QD

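### The low blood pressure rows in SAP 5.5.3 are built on each patient's maximum, so they miss patients with some low and some normal readings

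*SAP*

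**What the plan says.** SAP 5.5.3 defines two categorical blood pressure tables. The systolic one is introduced as "Percentage of patients with maximum systolic BP by category of BP post-baseline". Its lowest row is < 90, and its remaining rows step upward from 90 through 120, 140 and 160 to 180 mmHg. The diastolic one is "Percentage of patients with maximum diastolic BP by category of BP post-baseline (< 60, > 60, > 90, > 110, and > 120". Both classify a patient by the maximum. No table in the section uses the minimum.

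Readings are taken in three positions: "supine (after at least 5-min rest) and standing (after1-min and 3-min standing". Neither category table says which positions are used, or whether the post-baseline period stops at the end of treatment.

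The same section also plans "A separate table with a decrease in systolic BP > 20 mmHg, or diastolic > 10 mmHg on standing from supine position", at baseline and each later visit, with risk differences against placebo. It plans by-visit descriptive statistics as well; under SAP 3.1, "descriptive statistics will include the number of subjects (n), mean, SD, median, minimum, and maximum". Finally, "All vital signs data will be presented in a data listing".

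The protocol (Synopsis, Safety Analyses, and Section 8.3.4) commits to listing and summarising vital-sign values that are potentially clinically important (PCI) by criteria fixed in advance. SAP 5.5.3 labels no criteria as PCI. SAP Section 6, Table 4, does not record that the commitment was dropped.

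**The concern.** A table with a < 90 systolic row and a < 60 diastolic row looks as if it reports low blood pressure. Because the statistic is the maximum, one reading at or above the cut-off at any post-baseline visit takes the patient out of the low row. The off-drug follow-up visit can do this alone: a patient who is low at all four on-treatment visits and recovers after stopping is not counted.

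Supine and standing blood pressure is a named safety endpoint (Protocol 2.2.3, SAP 1.2.2). Exclusion criterion 11 gives numerical blood pressure limits only at the upper end, so patients with lowish pressure can enter. At stake is a descriptive safety count that would understate low pressure in every arm, and could be read as showing there was little of it.

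**Working it through.** The plan states no figure on this point, so there is nothing of its own to reproduce. The check has a logical part, which needs no assumption, and an illustration of size, which does.

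**Number of readings.** Protocol Table 1 marks vital signs at Days 7, 14, 28 and 42 and at 14 days after the last dose: 5 post-baseline visits. With 3 positions per visit there are up to 5 × 3 = 15 readings per patient if positions are pooled.

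**Logic.** For readings x1, …, xk and cut-off c:
- max(x1, …, xk) < c if and only if every reading is < c;
- at least one reading is < c if and only if min(x1, …, xk) < c.

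Example: systolic readings 118, 112, 84, 88, 115. The maximum is 118 and the minimum is 84. Two readings are below 90, yet the planned table puts the patient in the ≥ 90 row and not in < 90.

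**What else would count this patient?**
- The orthostatic table measures a fall from supine to standing. A patient who is low in both positions need not fall by > 20 or > 10 mmHg.
- By-visit statistics show the lowest value in each arm, not how many patients were below a threshold.
- The listing holds the values but no count.
- Adverse event tables (SAP 5.5.1) show low pressure only where it was reported as an event.

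By contrast, for laboratory tests that can be abnormal in two directions, SAP 5.5.2 presents both directions.

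**Illustration.** The documents give no blood pressure means or SDs, so all those used here are assumptions. Each reading is a patient mean (normal, between-patient SD sb) plus independent normal variation (within-patient SD sw), with no drug effect. There were 1,000,000 simulated patients per scenario. k = 5 is one reading per visit; k = 15 pools all positions.

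| Cut-off | Mean, sb, sw | k = 5: max below | k = 5: min below | k = 15: max below | k = 15: min below |
|---|---|---|---|---|---|
| Systolic 90 | 105, 12, 6 | 4.10% | 26.3% | 2.03% | 35.5% |
| Systolic 90 | 105, 10, 8 | 1.53% | 30.6% | 0.38% | 45.8% |
| Systolic 90 | 115, 10, 8 | 0.12% | 8.4% | 0.015% | 15.4% |
| Systolic 90 | 120, 8, 8 | 0.0014% | 1.7% | 0.0000% | 4.1% |
| Diastolic 60 | 70, 8, 6 | 2.83% | 36.7% | 0.86% | 51.8% |
| Diastolic 60 | 70, 6, 6 | 0.86% | 33.5% | 0.11% | 52.0% |
| Diastolic 60 | 75, 8, 6 | 0.67% | 18.5% | 0.16% | 29.8% |
| Diastolic 60 | 75, 6, 6 | 0.09% | 13.3% | 0.006% | 25.0% |

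Nine systolic scenarios were run (means 105, 115 and 120, each with three SD pairs). The four shown include the extremes. All four diastolic scenarios are shown.

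Within a scenario, the share of patients with any low reading whom the planned row would capture is P(max < c) / P(min < c). At k = 5 the highest share is 4.10 / 26.3 = 15.6% for systolic and 2.83 / 36.7 = 7.7% for diastolic. So in every scenario at least about 84% (systolic) or 92% (diastolic) of such patients are missed. With more readings, the planned row shrinks while the number of patients with a low reading grows. Readings at one visit are correlated in practice, so k = 15 with independent variation is an outer case.

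**The case against.** The strongest reply is that this is a high blood pressure table. The statistic is the maximum, the rows climb, and < 90 may be only the complement of ≥ 90. Nothing in SAP 5.5.3 calls it a hypotension count, and the row is labelled as a maximum. That is a fair reading of intent. It still leaves the plan with no table that counts patients with an absolute low value, and a near-empty < 90 row can be misread.

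Second, the orthostatic risk, which the eligibility criteria do address, is tabulated directly with confidence intervals. This stands, and it confines the point to absolute low pressure. The Phase 2b adverse events reported by at least 5% of liafensine patients (Protocol 1.2.1) include dizziness but not hypotension, so the documents do not flag absolute hypotension as an established problem.

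Third, the magnitude rests on assumed distributions. This also stands. The planned systolic row ranges from 0.001% to 4.1% across scenarios, so no single figure should be quoted as a forecast.

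Fourth, a minimum-based row is less specific. With no drug effect, 13% to 37% of patients enter the diastolic row at k = 5. This is a real, small downside, and it calls for reading the row against placebo.

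A reader might go further and infer that the plan cannot detect hypotension, or that the table will show none whatever the drug does. The documents do not support that. Pressure that is low at every reading would be counted, and falls on standing, by-visit minima, reported events and individual values remain visible.

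**Conclusion.** The point holds for two rows of two descriptive tables. As defined, the < 90 systolic and < 60 diastolic rows count only patients who are low throughout, follow-up included, and so understate how many had a low reading. This follows from the definition of a maximum and rests on no assumption. The size does: the paired percentages are conditional on assumed normal distributions and independent variation, and they show the contrast between maximum and minimum, not expected trial rates.

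The consequence is limited to safety reporting. No efficacy result, test or decision rule depends on these rows, and the underlying data are listed in full. The unmet PCI commitment is a related gap between protocol and SAP that the same change could help close.

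**What to change.** In SAP 5.5.3:
- Classify each patient's minimum post-baseline value for the existing < 90 systolic and < 60 diastolic categories, and keep the maximum for the high categories.
- Present both by position (supine, standing 1 min, standing 3 min).
- Show on-treatment visits separately from the visit 14 days after the last dose.
- Report by treatment arm against placebo, as the orthostatic table already does, so that the background rate in the minimum-based diastolic row is visible.
- State whether this table fulfils the PCI summary promised in Protocol 8.3.4. If not, give the PCI criteria or record the change in SAP Table 4.

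The cost is a few sentences and one extra derived variable for each pressure. The change needs no new data and affects no efficacy analysis. The cut-offs themselves stay as the SAP has them.

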- 11. Clinically significant vital sign abnormality at screening. This includes, but is not limited to, the following, in the supine (after at least 5 min rest) and standing (after 1 min and 3 min standing): systolic blood pressure ≥ 140 mmHg; diastolic blood pressure ≥ 90 mmHg; or heart rate < 50 or > 90 beats per minute. If the initial blood pressure is ≥ 140/90 mmHg, the lowest value from up to 3 additional attempts, which also must not be ≥ 140/90 mmHg, should be used. Patients with symptomatic orthostatic hypotension, at the discretion of investigator, will be excluded.
- 12. Corrected QT interval measurement according to the Fridericia rule (QTcF) > 450 msec for men and > 470 msec for women during controlled rest at screening, or history of long-QT syndrome.
- 13. ECGs containing any of the following readings:
  - Left bundle branch block
  - Right bundle branch block with QRS duration > 140 ms
  - Intraventricular conduction defect with QRS duration > 140 ms
  - Long QT syndrome
- 14. History of seizure, other than childhood febrile seizures.
- 15. History of clinically significant head trauma, including closed head injury with loss of consciousness, that is, in the opinion of the investigator, likely to affect central nervous system function.
- 16. History of clinically significant symptomatic orthostatic hypotension (ie, postural syncope).
- 17. History of narrow angle glaucoma.
- 18. History of cancer within 2 years prior to screening or between screening and baseline (Day -1), except for non-metastatic basal and/or squamous cell carcinoma of the skin.
- 19. Use of prescription or nonprescription medications for attention-deficit hyperactivity disorder (ADHD), narcolepsy, or cognitive enhancement (eg, methylphenidate, atomoxetine, modafinil, ginkgo biloba, and huperzine A) within 30 days prior to screening or between screening and baseline (Day -1).

- 20. Regular consumption of (eg, more days than not) excessive quantities of xanthine-containing beverages (eg, more than five cups of coffee or the equivalent per day) within 30 days prior to screening or between screening and baseline (Day -1).
- 21. Urine drug screen (UDS) positive for a drug of abuse, with the exception of cannabis in countries where it is legally available (see Table 3 for list of drugs of abuse). Where legal, prior use of cannabis is permitted provided the patient agrees to abstain from smoking or ingesting cannabis or cannabis products during the study.

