## 4.2. Subject Exclusion Criteria

Patients with any of the following characteristics/conditions will be excluded from study:

- 1. Prior participation in a study with liafensine.
- 2. Used any investigational drug product, device, or biologic within 3 months or 5 half-lives (whichever is longer) prior to baseline (Day -1).
- 3. A positive pregnancy test result or currently breastfeeding.
- 4. Clinically significant and/or unstable illness (including chronic, persistent, or acute infection), medical/surgical procedure, or trauma within 30 days prior to screening or between screening and baseline (Day -1) as determined by the investigator.
- 5. A history or presence of a clinically significant and/or unstable hepatic, renal, gastrointestinal, cardiovascular, endocrine, respiratory, immunologic, hematologic, dermatologic, or neurologic abnormality, or any other condition, that in the investigator's opinion, represents potential risk to the patient's safety and ability to fully participate in the study, or affects the absorption, distribution, metabolism, or excretion of liafensine.
- 6. Presence of autoimmune hepatitis, primary sclerosing cholangitis, untreated hepatitis C, active hepatitis B, or any other uncontrolled or unstable liver disease according to local guidance.
- 7. Uncontrolled human immunodeficiency virus (HIV) infection according to local guidance.
- 8. Uncontrolled abnormal thyroid function according to local guidance.
- 9. One or more clinical laboratory evaluations are outside the reference range, at screening, that are in the investigator's opinion, of potential risk to the patient's safety.
- 10. Has at the Screening Visit:
  - Alanine aminotransferase (ALT) or aspartate aminotransferase (AST) levels > 1.5x the upper limit of normal (ULN) at screening.
  - Total bilirubin (TBL) > 2 mg/dL (34.2 μmol/L) at screening, unless there is an explained indirect hyperbilirubinemia, eg, Gilbert's syndrome.
  - Alkaline phosphatase (ALP) > 1.5x the ULN at screening.

**Note**: Laboratory tests can be repeated to see if values return to normal range, but any such laboratory abnormality must be resolved by the Baseline Visit (Day -1).

11. Clinically significant vital sign abnormality at screening. This includes, but is not limited to, the following, in the supine (after at least 5 min rest) and standing (after 1 min and 3 min standing): systolic blood pressure ≥ 140 mmHg; diastolic blood pressure ≥ 90 mmHg; or heart rate < 50 or

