- > 90 beats per minute. If the initial blood pressure is  $\ge 140/90$  mmHg, the lowest value from up to 3 additional attempts, which also must not be  $\ge 140/90$  mmHg, should be used. Patients with symptomatic orthostatic hypotension, at the discretion of investigator, will be excluded.
- 12. Corrected QT interval measurement according to the Fridericia rule (QTcF) > 450 msec for men and > 470 msec for women during controlled rest at screening, or history of long-QT syndrome.
- 13. ECGs containing any of the following readings:
  - Left bundle branch block
  - Right bundle branch block with QRS duration > 140 ms
  - Intraventricular conduction defect with QRS duration > 140 ms
  - Long QT syndrome
- 14. History of seizure, other than childhood febrile seizures.
- 15. History of clinically significant head trauma, including closed head injury with loss of consciousness, that is, in the opinion of the investigator, likely to affect central nervous system function.
- 16. History of clinically significant symptomatic orthostatic hypotension (ie, postural syncope).
- 17. History of narrow angle glaucoma.
- 18. History of cancer within 2 years prior to screening or between screening and baseline (Day -1), except for non-metastatic basal and/or squamous cell carcinoma of the skin.
- 19. Use of prescription or nonprescription medications for attention-deficit hyperactivity disorder (ADHD), narcolepsy, or cognitive enhancement (eg, methylphenidate, atomoxetine, modafinil, ginkgo biloba, and huperzine A) within 30 days prior to screening or between screening and baseline (Day -1).
- 20. Regular consumption of (eg, more days than not) excessive quantities of xanthine-containing beverages (eg, more than five cups of coffee or the equivalent per day) within 30 days prior to screening or between screening and baseline (Day -1).
- 21. Urine drug screen (UDS) positive for a drug of abuse, with the exception of cannabis in countries where it is legally available (see Table 3 for list of drugs of abuse). Where legal, prior use of cannabis is permitted provided the patient agrees to abstain from smoking or ingesting cannabis or cannabis products during the study.
- 22. Use of potent inducers of CYP3A4 (eg, rifampin, rifabutin, phenytoin, carbamazepine, or phenobarbital) within 2 weeks prior to baseline (Day-1).
- 23. Current diagnosis or history of a psychotic disorder, MDD with psychotic features, manic or hypomanic episode of bipolar or related disorders.

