3.2. Definition of Baseline

Baseline value is defined as the last available value collected before the first dose date of study drug for all safety laboratory, safety ECG, vital sign, and efficacy values.

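### SAP 5.5.3 plans no change from baseline in blood pressure and no risk difference for the maximum-BP categories, and its ≥140 mmHg systolic row repeats the entry limit on the highest unconfirmed reading

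*SAP*

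**What the plan says.** **Entry.** Protocol 4.2, exclusion 11, excludes patients at screening with "systolic blood pressure ≥ 140 mmHg; diastolic blood pressure ≥ 90 mmHg", supine or standing. If the first reading is too high, "the lowest value from up to 3 additional attempts" is used.

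**Post-baseline BP outputs (SAP 5.5.3).**
- "Actual value of BP and HR, between supine and standing (after 1-min and 3-min standing) at each visit", by arm, with a figure of means by visit.
- "A separate table with a decrease in systolic BP > 20 mmHg, or diastolic > 10 mmHg on standing from supine position", with risk differences and 95% confidence intervals.
- "Percentage of patients with maximum systolic BP by category of BP post-baseline", in nested rows up to ≥140, ≥160 and ≥180, and a similar diastolic table with a boundary at 90. No position, confirmation, baseline category or risk difference is given.
- A listing.

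The heart-rate change table (>20 and >30) is also shown at baseline, so it cannot be a change from baseline.

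**Elsewhere.** SAP 3.2 defines baseline for "all safety laboratory, safety ECG, vital sign, and efficacy values". SAP 5.5.2 gives blood chemistry and haematology a change from baseline and a shift to the maximum, and gives liver tests risk differences. SAP 5.5.4 and 5.5.5 give change from baseline for C-SSRS and ECG, and QTcF has both absolute and increase criteria.

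**The concern.** Vital signs including BP are a named safety endpoint (Protocol 2.2.3), and comparing safety with placebo is an objective (Protocol 2.1.3). Liafensine inhibits norepinephrine and dopamine reuptake (Protocol 1.2), so a shift in BP is a fair question for this trial.

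The planned outputs answer it weakly, for two reasons. By-visit actual values carry the full spread between patients, which a baseline already in hand would largely remove. And the ≥140 row can be entered without any rise: a patient whose usual pressure lies just under the limit can be admitted on a low reading and counted later on a high one. With no baseline category beside it, the table cannot separate patients who moved up from those who were already there.

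**Working it through.** The plan states no rate or power for BP, so there is no figure of its own to reproduce.

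**Inputs from the documents.** About 180 patients randomised 1:1:1, so 120 liafensine and 60 placebo. Three readings per visit (supine, standing 1 min, standing 3 min; Protocol Table 1, note n). Vital signs on Days 7, 14, 28 and 42 and 14 days after the last dose: 5 × 3 = 15 scheduled readings, or 4 × 3 = 12 up to Day 42.

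**Assumptions, not in the documents.** Systolic readings are normal with a usual mean, a between-patient SD, a visit SD and a reading SD. There is no postural shift, attendance is full, and exclusion 11 is applied as written in each position. The maximum is taken over all positions.

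**Step 1: background in the upper rows, no drug effect (simulation).**

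| Mean / between / visit / reading SD | Visits | ≥140 | ≥160 |
|---|---|---|---|
| 114 / 11 / 5 / 4 | 4 | 7% | 0.0% |
| 122 / 11 / 8 / 4 (central) | 4 | 27% | 0.9% |
| 126 / 11 / 10 / 4 | 4 | 44% | 3.6% |
| 115 / 10 / 6 / 4 | 5 | 9.5% | 0.0% |
| 120 / 11 / 8 / 4 | 5 | 26% | 0.8% |
| 125 / 12 / 9 / 5 | 5 | 45% | 3.9% |

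The ≥180 row is about 0% throughout. If the maximum is supine only, the central 27% becomes 20%, so the unstated position matters. In the five-visit scenarios, 9% of patients (3% to 18%) already have a reading of 140 or more at the pre-dose visit.

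**Step 2: power for a true 5 mmHg rise at one visit, pooled liafensine against placebo, two-sided 0.05.**

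SE = SD × √(1/120 + 1/60) = SD × 0.158, and power ≈ Φ(5/SE − 1.96).

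Hand check, central case, ignoring the entry limit:
- Actual value: variance 11² + 8² + 4² = 201, SD 14.2, SE 2.24, 5/2.24 = 2.23, Φ(0.27) = 61%.
- Baseline-adjusted: correlation 121/201 = 0.60, residual SD 14.2 × √(1 − 0.60²) = 11.3, SE 1.79, 5/1.79 = 2.79, Φ(0.83) = 80%.

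With the entry limit applied in simulation, the SD is 13.5 and the correlation 0.56, giving a residual SD of 11.2. Power is then **65% on actual values and 81% baseline-adjusted**. At the four corners:

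| Mean, visit SD | Actual value | Baseline-adjusted |
|---|---|---|
| 114, 5 | 72% | 96% |
| 114, 10 | 55% | 67% |
| 126, 5 | 78% | 97% |
| 126, 10 | 58% | 68% |

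**Step 3: why adjusted and not raw change.** In the central case the SD of raw change is √(2 × (8² + 4²)) = 12.65, SE 2.0, Φ(2.5 − 1.96) = 71%. With visit SD 10 it is √(2 × (10² + 4²)) = 15.2, SE 2.41, Φ(2.08 − 1.96) = 55%. That is below the 58% for actual values at mean 126. Raw change helps description, but the dependable gain comes from adjusting for baseline.

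**The case against.** **No bias.** All randomised arms pass the same entry rule and are summarised by the same maximum, so the placebo column shows the background rate. This stands: the effect is dilution.

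**Only one row is affected.** A reader might infer from the shared 140 mmHg limit that noise fills the whole table. The documents do not support that. The SAP lists nested rows and defines none of them as a hypertension event, and ≥160 and ≥180 lie above the entry limit and stay nearly empty.

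**A rise criterion is not the remedy.** A reader might also want to count only patients at ≥140 who rose at least 20 mmHg from baseline. Centrally this lowers the background from about 27% to 10.6%, but it loses true risers too: power is about 0.55 against 0.56 for the plain row.

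**Other text touches the point.** SAP 3.4 mentions a summary of worst change from baseline, and Protocol 8.3.4 promises a summary of potentially clinically important vital signs. The first names no parameter and has no matching BP table in 5.5.3. The second has no criteria in either document, does not reappear in the SAP, and is not listed as a change in SAP Section 6. Neither fills the gap.

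**The simulation is approximate.** Protocol 7.1.2.1 requires vital-sign abnormalities to be resolved by the Baseline Visit. Applying the limit there as well lowers the central 27% to about 24.5%. The diastolic row is printed as >90, so it may not match the ≥90 exclusion exactly, although the symbol may be an extraction fault.

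**Safety analysis is descriptive.** No test of mean BP is planned, so power here only measures precision. By-visit means do show a shift by arm, but less precisely than the data allow.

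**Conclusion.** The omission is established by the text alone. SAP 5.5.3 uses the vital-sign baseline as a reference in no BP summary and gives no risk difference for the maximum-BP rows, unlike its treatment of other safety measures.

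The size rests on assumed BP variability. With no drug effect, about 27% of patients (7% to 44% over the four-visit scenarios) would fall in the ≥140 row. Adjusting for baseline raises power for a 5 mmHg rise from about 65% to 81% centrally, and it helped at every corner examined. The finding is a loss of precision and of individual-level interpretation. It is not a biased comparison and does not make the whole table uninformative. The change should be made before the analysis.

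**What to change.** In SAP 5.5.3:

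1. Summarise change from baseline in supine and standing systolic BP, diastolic BP and heart rate by visit and arm, with baseline-adjusted differences from placebo and 95% confidence intervals.
2. For the maximum-BP rows, add risk differences with 95% confidence intervals and a shift table from baseline category to maximum post-baseline category.
3. State which position, or positions, the maximum is taken over.

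The planned categories can stay. The cost is SAP wording and a few extra tables from readings already scheduled, with no new data.
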